8.5 Pregnancy and Postpartum Information

8.5.1 Participants Who Become Pregnant During the Trial

A pregnancy test must be performed before surgery for female patients, who are able to become pregnant. The patient group without surgery does not have to do the pregnancy test. Patients not able to become pregnant (male patients, female after menopause) do not have to have a pregnancy test. After surgery, the patient can become pregnant without any risk for her safety or for the efficacy of the study. If a patient wants to change to the surgery group, a pregnancy test must be performed before surgery. Pregnancy after surgery is not an AE.

8.5.2 Participants Whose Partners Become Pregnant

Participants, whose partners become pregnant is not an AE. The IMP has no systemic effect and thus does not affect reproductivity or child development. Pregnancy information of the partner will not be collected.

8.6 Medical Device Product Complaints for Drug/Device Combination Products

There is no medical device included.

8.6.1 Definition of Medical Device Product Complaints

n/a

8.6.2 Recording of Medical Device Product Complaints

n/a

8.6.3 Time Period and Frequency for Collecting Medical Device Product Complaints

n/a

8.6.4 Follow-Up of Medical Device Product Complaints

n/a

8.6.5 Regulatory Reporting Requirements for Medical Device Product Complaints

n/a

8.7 Pharmacokinetics

The IMP human cancellous bone has no pharmacokinetic action. It does not have systemic effects (Fachinformation point 5.1).

8.8 Genetics

No genetic information is recorded during the trial.

8.9 Biomarkers

No Biomarkers are collected during the trial.

8.10 Immunogenicity Assessments

There will be no immunogenicity assessment. The IMP is an authorized product and there are up to now no reports in respect to events regarding immunogenicity.

8.11 Medical Resource Utilisation and Health Economics

Medical resource utilization is minimal. The additional burden for the investigator is the explanation of the clinical trial to the patient and the filling of the documents related to the clinical trial.

The burden for the patient is the extended explication regarding the trial and the filling of the forms (KOOS, IKDC, CRF) during the visit. The patient must be compliant with the visit schedule, this could be an additional burden.

Regarding the health economics: There are no additional costs because of the trial. If the procedure shows efficacy and patient safety, the health system can save additional costs related to total meniscal transplantation or progression of osteoarthritis up to TKA. Additionally, the patient can work longer and does not need or only needs later support from the government.

9 STATISTICAL CONSIDERATIONS

Data analysis complies with ICH E9 Guideline and ICH E9(R1) Guideline. This clinical trial is to confirm patient safety and efficiency of the procedure.

For this reason, as primary objective PROMs (IKDC, KOOS and VAS-pain score) will be evaluated before surgery/at the beginning of the trial and then starting at 6 months after surgery/beginning of the trial for the operated or non-operated group, respectively. The evaluation will be performed also after 12 and 24 months and after 5 years. A primary analysis will be performed 2 years after surgery/start of the trial.

At the beginning of the trial and prior to operation demographic and baseline data will be collected and summarized for both groups.

For safety, there will be an evaluation of complications, AE, SAE and SUSARs at each follow-up visit (at the end of the hospital stay, after 6 weeks, after 6, 12, 24, months and after 5 years, for the operated group). The number of AE, SAE and SUSARs will be recorded and evaluated at each visit. MRI evaluation starts at the follow-up visit 6 weeks after surgery for the operated group and 24 months after the start of the trial for the non-operated group. The evaluation of the MRI will be performed after a modified graduation of Genovese et al. [32]. Additionally, there will be the meniscal size evaluated and if there is an extrusion of the meniscus and how big the extrusion is. There will be a Kaplan-Meier-time to event curve for both groups regarding progression of osteoarthritis up to TKA. The analysis will be conducted on all participant data after 2 years and after 5 years.

9.1 Analysis Sets

Full analysis set will be performed.

PROMs:

Change from baseline for the PROMs (IKDC, KOOS, VAS-pain score) for the operated/non-operated group after 6, 12 and 24 months and 5 years and between groups.

Complications, AE, SAE and SUSARs:

The number of complications, AE, SAE and SUSARs will be evaluated at each time point and compared between the groups with Fishers exact test.

MRI evaluation:

Change in MRI evaluated using the Outerbridge [1] graduation, the size of the meniscal defect and the meniscus itself, the MRI signal of the meniscus will be evaluated after a modified score after Genovese et al.[32] and the number of patients with an extrusion and the size of the extrusion.

Patient satisfaction:

Patient satisfaction will be categorized as: very pleased, pleased, not pleased, very unsatisfied and will be evaluated using the Chi-square test.

Progression of osteoarthritis up to TKA:

The number of patients with progression of osteoarthritis up to TKA for both groups will be compared with a Kaplan-Meier time to event curve.

9.2 Analyses Supporting Primary Objective(s)

The PROMs (IKDC, KOOS, VAS-pain score) may be considered as continuous numerical data. The PROMs

will be summarized by sample size N, mean, standard deviation (SD), minimum, first quartile Q1, median, third quartile and maximum. Box plots will be used to provide a graphical overview. If the numerical data are normally distributed an independent t-Test can be performed, if they are not normally distributed, a Mann-Whitney-U-Test must be used. Statistically significant differences will be assigned when $p < 0.05$.

9.2.1 Statistical Model, Hypothesis, and Method of Analysis

The change in PROMS from baseline in the operated and non-operated group will be compared by two-sided t-test for independent groups when data are normally distributed or with the Mann-Whitney-U-test.

The Null-hypothesis is that partial meniscal replacement does not improve mean PROMs for knee function in comparison to the non-operated group after 2 and 5 years.

The alternative hypothesis is that there that partial meniscal replacement does improve mean PROMs for knee function in comparison to the non-operated group after 2 and 5 years.

The PROMS should improve (Mean KOOS and IKDC should increase by at least 20 points, and VAS-pain score should decrease by at least 3 points, or to near zero, depending on the pre-surgical value).

Analysis of data will be performed by direct comparison of the groups at each time point and in comparison, to before surgery/start of the trial. Mean and standard deviation of the groups are compared. If there is a significant difference, the Null-Hypothesis will be rejected. Even when we have a loss of follow-up of 20% the power will still be 0.985. From our experience mean KOOS values presurgical are between 40-50 and between 50-60 for the IKDC, after treatment the expected improvement is to mean values between 80-90 for both scores. For the VAS-pain-score the presurgical mean value is around 4 and the post-surgical value is between 0 and 1. There is no risk of a type 1 error, because the values are measured several times over the follow-up period, thus there will be no false positive result. If the difference in the scores between pre- and post-surgery is lower than 18, the power is not big enough. Thus setting 20 as the difference for rejecting the Null-hypothesis is supported by enough power, even with only 8/24 patients in the respective group. The covariate could be smoking and sex. Smoking affects healing in general. It is not clear if there will be enough patients in each group to use these as confounders. Interactions will not be possible, because the treatment has no relation to any characteristic of the patient. There will be no adjustment made and no model fitting.

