9.8 Sample Size Determination

The unpaired t-Test will be used for normally distributed PROMs. Values for the primary outcome are expected to be about 55/84 for the IKDC score and 46/86 for the KOOS pre/postsurgery, respectively. For this calculation, the program G-power was used. A sample size of 9 in the operated group and 3 in the non-operated group would be sufficient to reach a power of 0.982. When we include 10 non-operated patients and 30 operated patients the effect size is 2.0, $\alpha = 0.00655$ and the power is than 0.993. If we have a 20% lost to follow-up, the numbers of patients will be 8/24 and $\alpha = 0.014$ and the power will be 0.985. The number of 30/10 is sufficient to reach a power of >0.8.

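### The normality-gated choice between a t-test of unstated variance form and Mann-Whitney leaves the primary type 1 error uncontrolled at 3:1 group sizes; Welch's test on change would fix it cheaply

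*Protocol*

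**What the plan says.** Three places in the Protocol describe the primary test.

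- Section 9.2 gives the rule for choosing it: "If the numerical data are normally distributed an independent t-Test can be performed, if they are not normally distributed, a Mann-Whitney-U-Test must be used". The significance threshold there is 0.05.
- Section 9.2.1 applies the rule to change from baseline, which "will be compared by two-sided t-test for independent groups when data are normally distributed or with the Mann-Whitney-U-test". Its null and alternative hypotheses are about mean PROMs. It rules out any adjustment or model.
- Section 9.8 sizes the trial on the same basis: "The unpaired t-Test will be used for normally distributed PROMs". It continues "When we include 10 non-operated patients and 30 operated patients the effect size is 2.0", with a stated power of 0.993 at alpha 0.00655. It then adds "If we have a 20% lost to follow-up, the numbers of patients will be 8/24", with a stated power of 0.985 at alpha 0.014.

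The text says independent or unpaired. It does not say pooled or Welch, names no normality test, gives no SD for either group, and does not mention unequal variances.

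**The concern.** A pooled-variance t-test tolerates unequal SDs when the groups are of equal size, but not when one group is three times the other. The pooled SD is then dominated by the larger group. If the small group is the more variable one, the standard error is too small and false positives rise; if it is the less variable one, the test is too strict and loses power.

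The gate adds a second weakness. It asks 8 to 10 controls to reveal non-normality, and then lets the answer change not only the test but the hypothesis, from a difference in means to a rank comparison. As nothing is adjusted or modelled, the whole primary inference rests on whichever test is chosen.

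**Working it through.** **Inputs.** Group sizes 30/10 and 24/8 and d = 2.0 come from section 9.8. Two-sided 0.05 comes from sections 9.2 and 9.2.1. The SD ratio of change (control / operated) is not in the protocol, so a range of 0.5 to 2 is assumed.

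**Step 1: the plan's own power.** Pooled-variance t-test, df = n1 + n2 − 2, noncentrality = d × √(n1·n2/(n1+n2)).

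- 10/30: 2.0 × √(300/40) = 5.477; df 38; alpha 0.00655 gives power 0.9935 (stated 0.993).
- 8/24: 2.0 × √(192/32) = 4.899; df 30; alpha 0.014 gives power 0.9857 (stated 0.985).

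Both reproduce with the pooled form.

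**Step 2: why 3:1 matters.** Set the operated SD to 1 and the control SD to r, at 30/10.

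- True variance of the mean difference: r²/10 + 1/30.
- Variance the pooled test assumes: [(9r² + 29)/38] × (1/10 + 1/30).
- r = 2: true 0.433, assumed 0.228. The standard error is √(0.228/0.433) = 0.73 of what it should be.
- r = 0.5: true 0.0583, assumed 0.1096. The standard error is 1.37 times what it should be.

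A normal approximation with the df 38 critical value of 2.024 gives 2 × [1 − Φ(2.024 × 0.725)] = 14% for r = 2 and 2 × [1 − Φ(2.024 × 1.371)] = 0.6% for r = 0.5.

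**Step 3: simulated type 1 error.** Normal data, no true difference, nominal two-sided 5%. The two-stage rule applies Shapiro-Wilk at 0.05 in each group, then pooled t or Mann-Whitney; the use of Shapiro-Wilk is an assumption.

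| Control SD / operated SD | Pooled t, 30/10 | Pooled t, 24/8 | Mann-Whitney, 24/8 | Two-stage rule, 24/8 | Welch, 24/8 |
|---|---|---|---|---|---|
| 0.5 | 0.9% | 0.9% | 2.0% | 1.2% | 5.0% |
| 0.76 | 2.6% | 2.7% | not run | not run | 5.1% |
| 1 | 4.9% | 4.9% | 4.7% | 5.1% | 5.2% |
| 1.25 | 7.9% | 7.9% | 6.2% | 7.7% | 5.2% |
| 1.5 | 10.6% | 10.9% | 7.4% | 10.8% | 5.3% |
| 2 | 15.5% | 15.7% | 9.6% | 15.6% | 5.2% |

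For contrast, the pooled test at 20/20 with a ratio of 2 gives 5.3%, so the imbalance in group size is what makes unequal SDs matter.

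**Step 4: what the normality check can see.** Shapiro-Wilk detects a gamma distribution with skewness 1.4 in 18% of samples of 8 and 24% of samples of 10. For an exponential distribution the figures are 33% and 45%.

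**Step 5: which direction is plausible for change scores.** Illustrative assumptions: baseline SD 15 in both groups; operated follow-up SD halved to 7.5 by a ceiling, correlation with baseline 0.2; control follow-up SD 15, correlation 0.7.

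- Operated SD of change: √(225 + 56.25 − 2 × 0.2 × 15 × 7.5) = √236.25 = 15.4.
- Control SD of change: √(225 + 225 − 2 × 0.7 × 225) = √135 = 11.6.
- Ratio 11.6/15.4 = 0.76, with pooled error of about 2.6%.

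Varying the operated follow-up SD (7.5 to 15), the operated correlation (0.2 to 0.4) and the control correlation (0.5 to 0.8) gave ratios of 0.53 to 1.08 and errors of 1.0% to 6.1%.

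**The case against.** The strongest reply is that the pooled test is not in the text. Welch's test is also an unpaired t-test, and a statistical analysis plan that is not shown could name it. That stands: the reproduced power shows how the trial was sized, not which form will be run, so the pooled error rates are conditional. It does not dispose of the point, because the protocol itself fixes the normality-gated switch to a test that does not match its hypothesis.

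Three stronger readings are tempting and are not supported.

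- **False positives are likely to be inflated.** A reader might argue that operated patients end near the top of the KOOS and IKDC scales, so their spread shrinks while the controls' does not. That concerns final scores. The quoted test is on change, where a ceiling at follow-up leaves the baseline spread in the difference, and stable controls may vary less. The argument could apply to the raw comparison at each time point that section 9.2.1 also mentions, but not to the change comparison.
- **The normality check causes the wrong error rate.** It does not. With normal data and equal SDs the two-stage rule gives about 5%, and at other ratios it tracks the pooled test.
- **The planned confidence interval is wrong too.** The protocol plans none for this comparison.

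It is also fair to say that patients choose their own group and nothing is adjusted, so confounding is the larger threat to the result. That limits how much this point matters, but does not make the stated rule a good one.

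**Conclusion.** The point holds as a cheap improvement. The protocol fixes a data-driven choice between a t-test of unstated variance form and a rank test that does not address its hypothesis about means, in groups where the smaller has only 8 to 10 patients.

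If the t-test is pooled, the nominal 5% could be anywhere from about 1% to 15% or 16% for SD ratios of 0.5 to 2, and at a modest ratio of 1.25 it is about 8%. Mann-Whitney does not cure this, and the gate gives little protection.

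The size rests on the assumed SD ratio, normal data in the simulations, and the pooled form being used. The direction is unknown, with a conservative test at least as plausible as an inflated one.

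**What to change.** In sections 9.2 and 9.2.1, name Welch's unequal-variance t-test on change from baseline as the single primary test, at two-sided 0.05, and report the mean difference with its 95% CI. Remove the normality-based choice. Keep Mann-Whitney or a permutation test as a sensitivity analysis only. Align the test named in section 9.8.

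The cost is a few words and a small loss of power if the SDs are in fact equal. At 24/8 and two-sided 0.05, power falls from about 0.66 to 0.61 at d = 1.0, from about 0.90 to 0.87 at d = 1.38, and from 0.997 to 0.993 at the planned d = 2.0.

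If the SDs differ, Welch's power moves with the true precision. With the operated SD twice the control SD and a difference of twice the control SD, power at 24/8 rises from 0.81 (pooled) to 0.94. With the control SD twice the operated SD and a difference of two operated SDs, it is 0.67 against 0.89, but the pooled figure is bought with an error rate near 16%.

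The change does nothing about confounding from patient-chosen groups, which needs separate treatment.

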3 TRIAL OBJECTIVES, ENDPOINTS AND ESTIMANDS

3.1 Primary Objective + Associated Endpoint and Estimand

| Primary Objective | Primary Endpoint |
|---------------------------------------|--|
| To evaluate efficacy of the procedure | Improvement of PROMs (KOOS, IKDC, VAS Pain Score) 2 and 5 years after surgery compared to scores of the non-operated group and compared to pre-surgery scores. |

Primary Estimand (Variable): Difference in PROMs after 2 and 5 years

Endpoint: 2 and 5 years after surgery/enrollment, or progression to TKA

Treatment: varies with the group chosen by the patient (operated or not operated)

Population: male and female patients between 18 and 60 years

Intercurrent event: progression of osteoarthritis up to TKA, lost to follow up, premature death, the patient wishes to change to the operated group after a certain time (The process: progression of osteoarthritis is very slow. It will be very unlikely that more than 1 patient wants to change to the operated group within the 5 years of the trial. The same is true for progression to TKA. The possibility to change later in the operated group will take off the pressure from the patient to make the “wrong” decision now.)

Population-level summary: The primary objective is to compare the PROM change from baseline between the operated and non-operated group after 2 and 5 years. The difference in obtained PROMS will be evaluated.

Estimand Description: The Estimand are the Difference in PROMs. This includes specific knee scores (IKDC, KOOS) and the VAS-Pain Score. IKDC and KOOS have values between 0 and 100 and the higher they are as better the function of the knee. The VAS Pain Score has values between 0 and 10 and the higher the score the higher the pain.

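### Section 9.2.1 gives two between-group contrasts for the primary null, change from baseline and scores at each visit, and in self-selected groups the second counts any persisting baseline gap as treatment effect

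*Protocol*

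**What the plan says.** Section 9.2.1 begins with one contrast: "The change in PROMS from baseline in the operated and non-operated group will be compared by two-sided t-test for independent groups", with a Mann-Whitney test if the data are not normal. Section 9.1 also lists change from baseline, within and between groups, and the population-level summary in 3.1 agrees: "The primary objective is to compare the PROM change from baseline between the operated and non-operated group after 2 and 5 years".

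Later in 9.2.1 there is a second description: "Analysis of data will be performed by direct comparison of the groups at each time point". The same sentence goes on to add a comparison with the values before surgery or at entry. The next two sentences are "Mean and standard deviation of the groups are compared" and "If there is a significant difference, the Null-Hypothesis will be rejected". The null itself is worded on means, not on change: "The Null-hypothesis is that partial meniscal replacement does not improve mean PROMs for knee function in comparison to the non-operated group". No sentence says which contrast decides.

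The split is not confined to 9.2.1. The primary endpoint, in both the synopsis and 3.1, sets the 2- and 5-year scores against those of the non-operated group and, separately, against the pre-surgery scores. The item labelled as the estimand variable in 3.1 is a difference in the scores at 2 and 5 years, without mention of change.

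Sections 4.1 and 6.6 leave the choice of group to the patient, without randomisation. On baseline differences, 9.2.1 says: "There will be no adjustment made and no model fitting".

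**The concern.** The two contrasts estimate the same quantity only if the groups start at the same level. Nothing in the design makes that likely. Patients with worse knees may be more inclined to choose surgery, or less, and the protocol gives expected baseline values for operated patients only.

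If follow-up scores are compared directly, a gap that was there at the start and persists is added in full to the apparent treatment effect. The null could be rejected when neither group has changed, or a real benefit could be masked. As both contrasts are written into the primary analysis, either could be reported as the deciding one. The investigator, who is also the sponsor, analyses unblinded data (4.1, 9.7), so that choice should be closed in advance.

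**Working it through.** **Inputs from the protocol**
- Group sizes: 30 operated and 10 non-operated; 24 and 8 after 20% loss (9.8).
- Analysis significance level: p < 0.05 (9.2), two-sided t-test (9.2.1).
- Planning effect size: d = 2.0. Pre/post planning values: IKDC 55/84, KOOS 46/86 (9.8).

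**Method.** Power of the pooled two-sided t-test from the noncentral t distribution, with df = n1 + n2 − 2 and noncentrality λ = d × √(n1·n2/(n1+n2)). The square root is √7.5 = 2.739 for 30/10 and √6 = 2.449 for 24/8.

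**The plan's own figures first.** With d = 2.0:
- 30/10: λ = 5.477; at α = 0.00655 power is 0.9935 (stated: 0.993).
- 24/8: λ = 4.899; at α = 0.014 power is 0.9857 (stated: 0.985).

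Both reproduce, so the method matches the plan's.

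**SD (assumption).** The protocol states none. If d = 2.0 rests on the planning differences, then 84 − 55 = 29 points gives SD = 29/2.0 = 14.5, and 86 − 46 = 40 points gives SD = 40/2.0 = 20.

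**Baseline gap (assumption).** Gaps b of 5 and 10 points, persisting in full, with no treatment effect. The expected raw-score difference at follow-up is then b, and the expected difference in change is 0. The raw-score rejection rate is the power at d = b/SD, two-sided 0.05:

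| Gap b | SD | d | λ, 30/10 | Rejects, 30/10 | λ, 24/8 | Rejects, 24/8 |
|---|---|---|---|---|---|---|
| 10 | 14.5 | 0.690 | 1.889 | 45% | 1.689 | 37% |
| 10 | 20 | 0.500 | 1.369 | 27% | 1.225 | 22% |
| 5 | 14.5 | 0.345 | 0.944 | 15% | 0.845 | 13% |
| 5 | 20 | 0.250 | 0.685 | 10% | 0.612 | 9% |

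**Change scores in the same settings.** In simulation (20,000 runs, 30/10, assumed baseline-to-follow-up correlation 0.5) the change-score test rejected in about 5% of runs throughout.

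**Masking.** If operated patients start 10 points lower and the gap persists, a true 20-point effect appears in raw scores as 20 − 10 = 10 points.

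**When the gap does not persist in full.** If half of a 10-point gap persists, the expected raw-score difference is +5 and the expected difference in change is 5 − 10 = −5. The two contrasts are then biased equally and in opposite directions.

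**Choice between the tests alone.** With no baseline gap, rejecting when either test is significant gave about 9% in the same simulation, instead of 5%.

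**The case against.** The strongest reply is that 9.2.1 fixes the variable in its first sentence, and that the later sentence is a loose statement of when the groups are compared. Its second half does refer back to baseline, and no sentence says outright that raw scores are tested. That reading is possible. However, the comparison with baseline is joined by *and* as something additional, the next sentence compares group means and SDs, and the rejection rule follows from that. The null, the 3.1 variable and the endpoint are also worded without change. At best the primary decision rule is ambiguous. An analysis plan that is not shown might name the deciding contrast, but the protocol would still state both.

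Other parts of the reply stand:
- The gaps and SDs are assumptions, and all the rejection rates assume that the gap persists in full, which is the case most favourable to change scores.
- A false result in favour of surgery needs the patients who choose surgery to start better. If they start worse, the bias works against surgery.
- A reader might infer much higher rates, 66% (24/8) to 76% (30/10), by taking SD = 10 from the 20-point improvement threshold divided by 2.0. The planning differences of 29 and 40 points do not imply an SD of 10.
- A reader might infer that 3.1 already defines the primary variable cleanly as change, so that a correction to 9.2.1 is enough. Only its population-level summary names change.

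**Conclusion.** The point holds as a contradiction in the primary decision rule, and should be corrected. Two contrasts are open to decide the null, and one of them carries any persisting baseline gap of self-selected groups into the result.

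With no treatment effect, a stable 10-point gap and SD 14.5 to 20, the raw-score test rejects in about 22-37% (24/8) or 27-45% (30/10); with a 5-point gap, in about 9-15%. Change scores stay near 5%. These figures illustrate the mechanism and do not predict the bias: without an SD or a baseline for the non-operated group, its actual size and direction cannot be known.

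A reader might also infer that change scores make the comparison sound. The protocol does not support that. Change scores remove a stable gap only, and self-selection remains with adjustment ruled out.

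**What to change.** - **9.2.1:** state that the null is tested only on the between-group difference in change from baseline at 2 and 5 years, and reword the null and the rejection rule to match. Make group means at each visit and within-group comparisons with baseline descriptive.
- **3.1 and synopsis:** reword the estimand variable and the primary endpoint to the same quantity, since a correction to 9.2.1 alone would leave the split in place.
- **Limit to state:** change from baseline does not remove regression to the mean or other confounding from patients choosing their group. A baseline-adjusted comparison would be the usual further step, and 9.2.1 at present excludes it.

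The cost is a few sentences in three places. No new data, visits or patients are needed.

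### The null in 9.2.1 is between groups, but the text does not stop a pre/post gain in the operated group from being used to reject it

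*Protocol*

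**What the plan says.** The hypothesis and the named test concern the two groups. Protocol 9.2.1 puts the null as "partial meniscal replacement does not improve mean PROMs for knee function in comparison to the non-operated group after 2 and 5 years". The changes from baseline "will be compared by two-sided t-test for independent groups when data are normally distributed or with the Mann-Whitney-U-test". The population-level summary in 3.1 agrees: "The primary objective is to compare the PROM change from baseline between the operated and non-operated group after 2 and 5 years".

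Other statements bring in a second contrast:

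- The primary endpoint in 1.1 and 3.1 is improvement "compared to scores of the non-operated group and compared to pre-surgery scores".
- Section 9.2.1 describes the analysis as "direct comparison of the groups at each time point and in comparison, to before surgery/start of the trial".
- The decision rule reads: "If there is a significant difference, the Null-Hypothesis will be rejected". It does not say which of the two comparisons the difference must come from.
- Later in the same section: "If the difference in the scores between pre- and post-surgery is lower than 18, the power is not big enough". From this the protocol concludes that 20 points is an adequately powered difference for rejecting the null, even with 8 and 24 patients.
- Section 9.8 names an unpaired t-test, but its expected values are all before and after surgery (IKDC 55 and 84, KOOS 46 and 86). It gives no expected value for the non-operated group.

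No sentence limits rejection to the between-group test, and none says that both comparisons must be significant.

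**The concern.** A pre/post comparison in the operated group tests whether the mean change in that group is zero. The protocol's null is that the change is no better than in the non-operated group. If both groups improve by the same amount, the first statement is false and the second is true, so a pre/post test says nothing about the stated hypothesis.

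Some shared improvement is plausible here. Patients enter with joint-line pain (5.3), medication is unrestricted (6.8), physiotherapy is allowed (6.8.4), and the PROMs are self-reported without blinding (4.1, 6.6.3). The non-operated group is there to account for such changes. The pre/post contrast is also the easier one to pass, because it uses up to 30 operated patients and does not depend on the 10 controls. The investigator, who is also the sponsor, plans to run the analysis (9.7, 10.4). It should therefore be settled in advance which contrast decides the primary claim.

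**Working it through.** **The plan's own power figures.** For a two-sided unpaired t-test, the noncentrality is d × √(n₁n₂/(n₁+n₂)).

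- 10/30 patients, d = 2.0, alpha 0.00655: 2.0 × √(300/40) = 5.477, 38 degrees of freedom, critical value 2.877, power 0.9935 (stated 0.993).
- 8/24 patients, d = 2.0, alpha 0.014: 2.0 × √(192/32) = 4.899, 30 degrees of freedom, critical value 2.610, power 0.9857 (stated 0.985).

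These two figures are sound as arithmetic for a between-group test. The question is which contrast decides.

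**Inputs for the pre/post route.**

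- n = 30 operated patients, or 24 after 20% loss (9.8); two-sided p < 0.05 (9.2).
- SD of change: not given, so assumed. Dividing the expected rises in 9.8 by the stated effect size gives 29/2.0 = 14.5 (IKDC) and 40/2.0 = 20 (KOOS).
- Gain shared by both groups: not given, so varied from 0 to 29 points. The between-group null is true in every row below.

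**Formula.** One-sample t-test on change, with noncentrality (gain/SD) × √n. Two examples with n = 30 (29 degrees of freedom, critical value 2.045):

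- Gain 5, SD 14.5: 5/14.5 × √30 = 1.889, rejection 0.447.
- Gain 10, SD 20: 10/20 × √30 = 2.739, rejection 0.754.

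**Adding the 20-point value.** If the observed mean gain must also reach 20 points, that condition dominates: with SD 20, a mean of 20 has t of about 20/(20/√30) = 5.5. The rejection rate is then close to 1 − Φ((20 − gain)/(SD/√n)). For gain 10 and SD 20 this is 1 − Φ(2.739) = 0.003.

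Results for 30 operated patients with equal true change in both groups:

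| Shared gain | Pre/post test, SD 14.5 | Pre/post test, SD 20 | And mean gain ≥ 20, SD 14.5 | And mean gain ≥ 20, SD 20 |
|---|---|---|---|---|
| 0 | 5% | 5% | 0% | 0% |
| 5 | 45% | 26% | <0.1% | <0.1% |
| 10 | 95% | 75% | <0.1% | 0.3% |
| 15 | >99.9% | 98% | 3.0% | 8.5% |
| 20 | 100% | >99.9% | 50% | 50% |
| 29 | 100% | 100% | >99.9% | 99.3% |

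With 24 operated patients, the pre/post test alone rejects 22 to 37% of the time at 5 points and 65 to 90% at 10. With the 20-point condition it rejects under 1% at 10 points, 5 to 11% at 15, and about 50% at 20.

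**Between-group test.** With equal true change its noncentrality is zero, so it rejects 5% of the time in every row (0.047 to 0.053 in simulation).

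**Sensitivity to the SD.** Dividing the protocol's 20-point difference by 2.0 gives an SD of 10. At n = 30 the pre/post test alone then rejects 75% of the time at 5 points and over 99.9% at 10. With the 20-point condition it rejects 0.3% at 15 points and 50% at 20.

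**The case against.** There is a good case that the protocol already means a between-group decision. Every test named for the primary outcome is for independent groups. The null, the alternative and the population-level summary are all between-group. The sentence directly before the rejection rule says that the groups' means and standard deviations are compared, so the difference in that rule most naturally refers to the groups. The endpoint joins its comparators with *and*, which could mean that both are required; that would be stricter than the between-group test alone. All this stands as a possible reading. The protocol does not fix it, and the 20-point rejection value is argued from the pre/post difference in the same paragraph.

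The protocol names no paired test, so the paired calculation is an illustration. Treating the pre and post scores as two independent samples of 30, with the same range used as the SD of the scores, gives 16 to 26% at a shared 5 points and 48 to 75% at 10. These rates are lower but still far above 5%. The 20-point condition is the stronger reply: where it applies, it nearly removes the problem for shared gains up to 10 points. Section 2.2 also expects very little improvement without surgery, though it gives no figure.

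Two further inferences may tempt a reader, and the text supports neither:

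- That a significant worsening would also count, because the rejection sentence gives no direction. The alternative hypothesis says that replacement improves the scores, and the paragraph asks for KOOS and IKDC to rise and VAS pain to fall.
- That the rule would miss a graft that only prevents deterioration. This would require the pre/post test to replace the between-group test, and nothing says that it does.

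**Conclusion.** The point holds as an ambiguity in the decision rule, and it should be fixed. The hypothesis is between-group, but the endpoint, the unnamed contrast in the rejection sentence and the origin of the 20-point value permit a pre/post gain in operated patients to be used to reject it.

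A reader might go further and say that the protocol declares efficacy whenever both groups improve equally. The documents do not support that, because a coherent between-group reading exists.

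The size depends on how the text is applied. With 30 operated patients and equal true change, the pre/post test alone rejects 26 to 45% of the time at a shared gain of 5 points and 75 to 95% at 10. With the 20-point condition, it rejects at most 0.3% at 10 points, roughly 3 to 8.5% at 15, about 50% at 20, and near 100% at 29, which is the rise expected for IKDC after surgery. The between-group test stays at 5%. The figures rest on an assumed SD of change of 14.5 to 20 points and on assumed shared gains, because the protocol gives neither an SD nor an expected value for the non-operated group.

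**What to change.** - In 1.1 and 3.1, limit the primary endpoint to the difference between the operated and non-operated groups in change from baseline.
- In 9.2.1, state that the null is rejected only if that between-group difference is significant and favours the operated group.
- In 9.2.1, label the pre/post changes within each group, and the 20-point gain, as descriptive: mean change with a 95% confidence interval, with no efficacy conclusion drawn from them.

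The change is to wording only; no patients, visits or data are added. The planned numbers can stay: at a true between-group effect size of 2.0 and two-sided 0.05, power is 0.9996 with 10/30 patients and 0.997 with 8/24. That effect size is the protocol's own assumption and is not backed by a control-group figure. The small cost is that the pre/post improvement can no longer be presented as a primary result.
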